APPENDIX 7: DAIDS TABLE FOR GRADING SEVERITY OF ARTHRALGIA ADVERSE EVENTS

[figure not shown]
The following excerpt from the DAIDS AE Grading Table Corrected (Version 2.1-July 2017) will be used to grade reported events of joint pain (arthralgia). Solicited AEs involving arthralgias will be graded using the arthralgia criteria whereas unsolicited AEs involving arthralgias will be graded using the appropriate row based on the presence of symptoms.

[figure not shown]
PARAMETER	GRADE 1 MILD	GRADE 2 MODERATE	GRADE 3 SEVERE	GRADE 4 POTENTIALLY LIFE- THREATENING
Arthralgia	Joint pain causing no or minimal interference with usual social & functional activities	Joint pain causing greater than minimal interference with usual social & functional activities	Joint pain causing inability to perform usual social & functional activities	Disabling joint pain causing inability to perform basic self-care functions
Arthritis (objective findings on PE corresponding to the joint pain)	Stiffness or joint swelling causing no or minimal interference with usual social & functional activities	Stiffness or joint swelling causing greater than minimal interference with usual social & functional activities	Stiffness or joint swelling causing inability to perform usual social & functional activities	Disabling joint stiffness or swelling causing inability to perform basic self-care functions

APPENDIX 9: ROLES AND RESPONSIBILITIES

Principal Investigator

The PI is responsible for the conduct of the RV 508 study at MUWRP. This is the person designated as taking overall responsibility within the team of researchers for the conduct and reporting of the RV 508 study. The PI will help prepare study reports and article(s) for publication in collaboration with the protocol team. In addition, the PI is responsible for the day-to-day running of the research project.

The PI is responsible for ensuring that:

- The dignity, rights, safety and well-being of participants are given priority at all times.
- The study has obtained IRB approval prior to commencement
- All necessary submissions are made to the local IRB, as applicable
- The study will be conducted by the PI personally and/or members of his/her research team
- Each member of the research team, including PI, who has direct involvement with research participants and/or person-identifiable data, has completed all required training
- Procedures are in place to ensure collection of high quality, accurate data
- Serious Adverse Events and unanticipated problems will be reported to the required IRBs and PSRT
- Accurate records will be maintained and made available as required
- Continuing Review Reporting requirements are completed
- Counseling occurs for participants on HIV and pregnancy
- The consenting of participants is done correctly and prior to any study procedures

Associate Investigators

To act for the PI when the latter is unable to discharge their responsibilities owing to travel, leave, deployment, or other extenuating circumstances.

To assist the PI in all aspects of protocol execution.

Study Pharmacist

- Responsible for administering, dispensing, and accountability of study drug; assessment and management of adverse events; and review of arising data queries.

Laboratory Investigator

- Laboratory Investigator supervises clinical (CAP certified) and research laboratory activities for the study.
- Laboratory investigators will not have contact with study participants or personal identifiers and agree not to attempt to obtain any individually identifiable participant data

DoD Research Monitor

The DoD Research Monitor may perform oversight functions (e.g. observe recruitment, enrollment procedures, and the consent process for participants; oversee study interventions and interactions; review monitoring plans and UPIRTSO reports; oversee data collection, and analysis) and report their observations and findings to the IRB. The DoD research monitor may discuss the research protocol with the investigators, interview participants, and consult with others outside of the study about the research. The research monitor shall have authority to stop a research protocol in progress, remove individual participants from a research protocol, and take

whatever steps are necessary to protect the safety and well-being of participants until the IRBs can assess the monitor's report. Research Monitors shall have the responsibility to promptly report their observations and findings to the IRB. The DoD Research Monitor is required to review all unanticipated problems involving risks to subjects or others, serious adverse event (SAE) reports, and all participant deaths. The DoD Research Monitor at a minimum must comment on the outcomes of the event or problem and in case of a serious adverse event or death, comments on the relationship to participation in the study. They must also indicate whether he/she concurs with the details of the report provided by the PI.

The DoD Research Monitor should review all initial reports for SAEs, unanticipated problems involving risks to subjects or others, and all participant deaths in a timely manner (within 48 hours), and provide their own independent report. The Research Monitor will provide an unbiased written report of all unanticipated problems involving risks to subjects or others, and related SAEs and deaths, within 10 working days to the MUSPH IRB, NDA (where applicable), the sponsor, and to the WRAIR HSPB by phone [REDACTED] or by email [REDACTED]. All Research Monitor reports for unrelated SAEs and deaths should be kept with the corresponding SAE reports at the study site.

The WRAIR HSPB will submit copies of these reports to the USAMRDC ORP HRPO as per SOP UWZ-C-636.

IND Medical Officer

The IND Medical Officer reviews and keeps abreast of adverse events and study pauses that may occur during the study (all adverse events, including deaths and serious or unexpected side effects, are reported to the IND Medical Officer via the PI) in order to ensure accurate and timely reporting to the FDA.

Clinical Research Staff

Under the guidance and supervision of the investigator, the duties of the Clinical Research Staff may include the following:

- Assisting in training other site personnel and other medical staff in understanding and implementing the protocol
- Recruiting and screening the potential study participants according to the protocol's inclusion and exclusion criteria
- Maintaining adequate source documentation (any document, or record where participant data are first recorded). All data noted in the CRF should be verifiable by supporting source documentation [21 CFR 312.62(b)]
- Completing the CRFs for the study accurately and completely as determined by the investigator
- Maintaining records of participant status in the study by using tools such as the enrollment log CRFs, etc.

WRAIR/MHRP/VRC Consultants

- Will serve as a liaison between the site and Sponsor
- Responsible for providing input for the study design and protocol development
- To oversee the process of study implementation, management, and monitoring to include data collection

- Serve as technical advisors and subject matter experts for study execution
- Agree not to attempt to obtain any individually identifiable participant data

VRC IND Representatives

- Will serve as the point of contact on behalf of the sponsor for the IND
- Responsible for ensuring compliance with the protocol and applicable US FDA regulations
- Assumes the responsibilities of the sponsor as detailed in 21 CFR 312 Subpart D
- Will not have contact with study participants and agree not to attempt to obtain any individually identifiable participant data

APPENDIX 10: DIARY CARD

[figure not shown]

RV 508 Participant Diary Card

**Makerere University Walter Reed Project
Kampala, Uganda**

**Version 1.5
03 March 2020**

Participant ID

Participant ID

General Symptoms Severity Scale

None= you have no symptoms

Mild= minimal symptoms; cause minimal or no interference with work, school, or self care activities.

Moderate=notable symptoms; required modification in activity; did not result in loss of work or cancellation of social activities

Severe = incapacitating symptoms; requiring bed rest and/or resulted in loss of work or cancellation of social activities.

[figure not shown]
[figure not shown]
[figure not shown]
For any Problems Call:

Injection Site Pain Severity Scale

How to Measure Swelling and Redness at the Injection Site

1. Determine the widest part (or diameter) of the area.
2. Using the ruler that the clinic staff gave to you, measure the widest part of the area in centimeters (cm) as shown on the pictures below. Each small hash mark on the centimeter ruler equals one tenth (0.1) of a centimeter.
3. Measure the swelling (raised area) and the redness (red area) separately and record each measurement on the diary card.

Please complete this diary in black or blue ink only

Participant ID

Day of Vaccination

Date: ____/____/____ (dd/mmm/yyyy)

The evening of the day of Vaccination:

Temp: _____ (oral, °C) Time Taken: _____ PM

If you have a fever and wish to take your temperature again, record your additional temperature:

Temp: _____ (oral, °C) Time Taken: _____ AM / PM (circle)

Temp: _____ (oral, °C) Time Taken: _____ AM / PM (circle)

Are you taking any medication? Yes No

If yes, please list medication(s):

Please use the symptom scale at the bottom of the page

Gen. Symptoms	None	Mild	Moderate	Severe
Joint Pain				
Feeling Unwell				
Muscle Aches (not at injection site)				
Headache				
Chills				
Nausea				

Injection Site Symptoms	None	Mild	Moderate	Severe
Local Pain				
Swelling Measure in cm	____. __ cm		Please record in cm, the largest width measurement of the swelling (Example: 2.5 cm)	
Redness Measure in cm	____. __ cm		Please record in cm, the largest width measurement of the redness (Example: 2.5 cm)	

Symptoms Severity Scale**None** = no symptoms**Mild** = minimal symptoms; cause minimal or no interference with work, school, or self care activities.**Moderate** = notable symptoms; required modification in activity or medication; did not result in loss of work or cancellation of social activities.**Severe** = incapacitating symptoms; requiring bed rest and/or resulted in loss of work or cancellation of social activities.**For any problems call:** [REDACTED]**Injection Site Pain Severity Scale****None** = no pain**Mild** = minimal pain; no limitation of use of arm**Moderate** = notable pain; some limitation of use of arm**Severe** = extreme pain; complete limitation of use of arm

Participant ID

Day 1 after Vaccination

Date: ___/___/___ (dd/mmm/yyyy)

Temp: _____ (oral, °C) Time Taken: _____ AM / PM (circle)

If you have a fever and wish to take your temperature again, record your additional temperature:

Temp: _____ (oral, °C) Time Taken: _____ AM / PM (circle)

Temp: _____ (oral, °C) Time Taken: _____ AM / PM (circle)

Are you taking any medication? Yes No

If yes, please list medication(s):

Please use the symptom scale at the bottom of the page

Gen. Symptoms	None	Mild	Moderate	Severe
Joint Pain				
Feeling Unwell				
Muscle Aches (not at injection site)				
Headache				
Chills				
Nausea				

Injection Site Symptoms	None	Mild	Moderate	Severe
Local Pain				
Swelling Measure in cm	___ . __ cm		Please record in cm, the largest width measurement of the swelling (Example: 2.5 cm)	
Redness Measure in cm	___ . __ cm		Please record in cm, the largest width measurement of the redness (Example: 2.5 cm)	

Symptoms Severity Scale

None = no symptoms

Mild = minimal symptoms; cause minimal or no interference with work, school, or self care activities.

Moderate = notable symptoms; required modification in activity or medication; did not result in loss of work or cancellation of social activities.

Severe = incapacitating symptoms; requiring bed rest and/or resulted in loss of work or cancellation of social activities.

For any problems call:

Injection Site Severity Scale

None = no symptoms

Mild = minimal pain; no limitation of use of arm

Moderate = notable pain; some limitation of use of arm

Severe = extreme pain; complete limitation of use of arm

Participant ID

Day 2 after Vaccination

Date: ____/____/____ (dd/mmm/yyyy)

Temp: _____ (oral, °C) Time Taken: _____ AM / PM (circle)

If you have a fever and wish to take your temperature again, record your additional temperature:

Temp: _____ (oral, °C) Time Taken: _____ AM / PM (circle)

Temp: _____ (oral, °C) Time Taken: _____ AM / PM (circle)

Are you taking any medication? Yes No

If yes, please list medication(s):

Please use the symptom scale at the bottom of the page

Gen. Symptoms	None	Mild	Moderate	Severe
Joint Pain				
Feeling Unwell				
Muscle Aches (not at injection site)				
Headache				
Chills				
Nausea				

Injection Site Symptoms	None	Mild	Moderate	Severe
Local Pain				
Swelling Measure in cm	____. __ cm		Please record in cm, the largest width measurement of the swelling (Example: 2.5 cm)	
Redness Measure in cm	____. __ cm		Please record in cm, the largest width measurement of the redness (Example: 2.5 cm)	

Symptoms Severity Scale**None** = no symptoms**Mild** = minimal symptoms; cause minimal or no interference with work, school, or self care activities.**Moderate** = notable symptoms; required modification in activity or medication; did not result in loss of work or cancellation of social activities.**Severe** = incapacitating symptoms; requiring bed rest and/or resulted in loss of work or cancellation of social activities.**For any problems call:** [REDACTED][REDACTED]**Injection Site Severity Scale****None** = no symptoms**Mild** = minimal pain; no limitation of use of arm**Moderate** = notable pain; some limitation of use of arm**Severe** = extreme pain; complete limitation of use of arm

Participant ID

Day 3 after Vaccination

Date: ____/____/____ (dd/mmm/yyyy)

Temp: _____ (oral, °C) Time Taken: _____ AM / PM (circle)

If you have a fever and wish to take your temperature again, record your additional temperature:

Temp: _____ (oral, °C) Time Taken: _____ AM / PM (circle)

Temp: _____ (oral, °C) Time Taken: _____ AM / PM (circle)

Are you taking any medication? Yes No

If yes, please list medication(s):

Please use the symptom scale at the bottom of the page

Gen. Symptoms	None	Mild	Moderate	Severe
Joint Pain				
Feeling Unwell				
Muscle Aches (not at injection site)				
Headache				
Chills				
Nausea				

Injection Site Symptoms	None	Mild	Moderate	Severe
Local Pain				
Swelling Measure in cm	____. __ cm		Please record in cm, the largest width measurement of the swelling (Example: 2.5 cm)	
Redness Measure in cm	____. __ cm		Please record in cm, the largest width measurement of the redness (Example: 2.5 cm)	

Symptoms Severity Scale

None = no symptoms

Mild = minimal symptoms; cause minimal or no interference with work, school, or self care activities.

Moderate = notable symptoms; required modification in activity or medication; did not result in loss of work or cancellation of social activities.

Severe = incapacitating symptoms; requiring bed rest and/or resulted in loss of work or cancellation of social activities.

For any problems call: [REDACTED]

Injection Site Severity Scale

None = no symptoms

Mild = minimal pain; no limitation of use of arm

Moderate = notable pain; some limitation of use of arm

Severe = extreme pain; complete limitation of use of arm

Participant ID

Day 4 after Vaccination

Date: ___/___/___ (dd/mmm/yyyy)

Temp: _____ (oral, °C) Time Taken: _____ AM / PM (circle)

If you have a fever and wish to take your temperature again, record your additional temperature:

Temp: _____ (oral, °C) Time Taken: _____ AM / PM (circle)

Temp: _____ (oral, °C) Time Taken: _____ AM / PM (circle)

Are you taking any medication? Yes No

If yes, please list medication(s):

Please use the symptom scale at the bottom of the page

Gen. Symptoms	None	Mild	Moderate	Severe
Joint Pain				
Feeling Unwell				
Muscle Aches (not at injection site)				
Headache				
Chills				
Nausea				

Injection Site Symptoms	None	Mild	Moderate	Severe
Local Pain				
Swelling Measure in cm	___ . __ cm		Please record in cm, the largest width measurement of the swelling (Example: 2.5 cm)	
Redness Measure in cm	___ . __ cm		Please record in cm, the largest width measurement of the redness (Example: 2.5 cm)	

Symptoms Severity Scale

None = no symptoms

Mild = minimal symptoms; cause minimal or no interference with work, school, or self care activities.

Moderate = notable symptoms; required modification in activity or medication; did not result in loss of work or cancellation of social activities.

Severe = incapacitating symptoms; requiring bed rest and/or resulted in loss of work or cancellation of social activities.

For any problems call:

Injection Site Severity Scale

None = no symptoms

Mild = minimal pain; no limitation of use of arm

Moderate = notable pain; some limitation of use of arm

Severe = extreme pain; complete limitation of use of arm

Participant ID

Day 5 after Vaccination

Date: ____/____/____ (dd/mmm/yyyy)

Temp: _____ (oral, °C) Time Taken: _____ AM / PM (circle)

If you have a fever and wish to take your temperature again, record your additional temperature:

Temp: _____ (oral, °C) Time Taken: _____ AM / PM (circle)

Temp: _____ (oral, °C) Time Taken: _____ AM / PM (circle)

Are you taking any medication? Yes No

If yes, please list medication(s):

Please use the symptom scale at the bottom of the page

Gen. Symptoms	None	Mild	Moderate	Severe
Joint Pain				
Feeling Unwell				
Muscle Aches (not at injection site)				
Headache				
Chills				
Nausea				

Injection Site Symptoms	None	Mild	Moderate	Severe
Local Pain				
Swelling Measure in cm	____. __ cm		Please record in cm, the largest width measurement of the swelling (Example: 2.5 cm)	
Redness Measure in cm	____. __ cm		Please record in cm, the largest width measurement of the redness (Example: 2.5 cm)	

Symptoms Severity Scale**None** = no symptoms**Mild** = minimal symptoms; cause minimal or no interference with work, school, or self care activities.**Moderate** = notable symptoms; required modification in activity or medication; did not result in loss of work or cancellation of social activities.**Severe** = incapacitating symptoms; requiring bed rest and/or resulted in loss of work or cancellation of social activities.**For any problems call:** 
**Injection Site Severity Scale****None** = no symptoms**Mild** = minimal pain; no limitation of use of arm**Moderate** = notable pain; some limitation of use of arm**Severe** = extreme pain; complete limitation of use of arm

Participant ID

Day 6 after Vaccination

Date: ___/___/___ (dd/mmm/yyyy)

Temp: _____ (oral, °C) Time Taken: _____ AM / PM (circle)

If you have a fever and wish to take your temperature again, record your additional temperature:

Temp: _____ (oral, °C) Time Taken: _____ AM / PM (circle)

Temp: _____ (oral, °C) Time Taken: _____ AM / PM (circle)

Are you taking any medication? Yes No

If yes, please list medication(s):

Please use the symptom scale at the bottom of the page

Gen. Symptoms	None	Mild	Moderate	Severe
Joint Pain				
Feeling Unwell				
Muscle Aches (not at injection site)				
Headache				
Chills				
Nausea				

Injection Site Symptoms	None	Mild	Moderate	Severe
Local Pain				
Swelling Measure in cm	___ . __ cm		Please record in cm, the largest width measurement of the swelling (Example: 2.5 cm)	
Redness Measure in cm	___ . __ cm		Please record in cm, the largest width measurement of the redness (Example: 2.5 cm)	

Symptoms Severity Scale

None = no symptoms

Mild = minimal symptoms; cause minimal or no interference with work, school, or self care activities.

Moderate = notable symptoms; required modification in activity or medication; did not result in loss of work or cancellation of social activities.

Severe = incapacitating symptoms; requiring bed rest and/or resulted in loss of work or cancellation of social activities.

For any problems call:

Injection Site Severity Scale

None = no symptoms

Mild = minimal pain; no limitation of use of arm

Moderate = notable pain; some limitation of use of arm

Severe = extreme pain; complete limitation of use of arm

Participant ID

Day 7 after Vaccination

Date: ____/____/____ (dd/mmm/yyyy)

Temp: _____ (oral, °C) Time Taken: _____ AM / PM (circle)

If you have a fever and wish to take your temperature again, record your additional temperature:

Temp: _____ (oral, °C) Time Taken: _____ AM / PM (circle)

Temp: _____ (oral, °C) Time Taken: _____ AM / PM (circle)

Are you taking any medication? Yes No

If yes, please list medication(s):

Please use the symptom scale at the bottom of the page

Gen. Symptoms	None	Mild	Moderate	Severe
Joint Pain				
Feeling Unwell				
Muscle Aches (not at injection site)				
Headache				
Chills				
Nausea				

Injection Site Symptoms	None	Mild	Moderate	Severe
Local Pain				
Swelling Measure in cm	___. __ cm		Please record in cm, the largest width measurement of the swelling (Example: 2.5 cm)	
Redness Measure in cm	___. __ cm		Please record in cm, the largest width measurement of the redness (Example: 2.5 cm)	

Symptoms Severity Scale

None = no symptoms

Mild = minimal symptoms; cause minimal or no interference with work, school, or self care activities.

Moderate = notable symptoms; required modification in activity or medication; did not result in loss of work or cancellation of social activities.

Severe = incapacitating symptoms; requiring bed rest and/or resulted in loss of work or cancellation of social activities.

For any problems call: [REDACTED]

Injection Site Severity Scale

None = no symptoms

Mild = minimal pain; no limitation of use of arm

Moderate = notable pain; some limitation of use of arm

Severe = extreme pain; complete limitation of use of arm

Participant ID

If you have any of the General or Injection Site Symptoms that is still ongoing after day 7, please complete stop dates below.

General Symptoms	Date the Symptom Ended	Maximum severity after day 7 (Mild, moderate or severe)
Joint Pain		
Feeling Unwell		
Muscle Aches (not at injection site)		
Headache		
Chills		
Nausea		

Injection Site Symptoms	Date the Symptom Ended	Maximum severity after day 7 (Mild, moderate or severe)
Local pain		
Swelling Measure in cm		__ __. __ cm
Redness Measure in cm		__ __. __ cm

Are you or have you taken any medication after day 7? If so, please record the name of the medication and the date you stopped taking the medication below, if applicable.

Name of Medication	Date You Stopped Medication

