Follow-up on participant well-being will be performed by telephone or clinic visit on the day following vaccination and by clinic visit on Day 3 following the injection to assess their clinical status. Participants may call or come to the clinic at any time-point for evaluation, if they experience unusual, moderate or severe signs and symptoms. Diary cards will be reviewed with the clinician at any visit from day of vaccination through the first study visit following completion of the diary card. If upon reviewing the clinician finds that general symptom or injection site symptom information (except swelling or redness measurements) is missing from the diary cards, the participant will be asked to provide the missing information to the best of their recollection.

At every visit through study day 28, all participants will be asked about other interim adverse experiences, which will be recorded in source documents and entered into the study database within 3 business days. After study day 28, only serious adverse events and new chronic medical conditions that require ongoing medical management will be recorded in source documents and entered into the database, through the last study visit. All other adverse events will be recorded on source documents only. The PI or designee will assess the relationship of the study product to the events.

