8.3.2 Safety Analysis

Safety and tolerability will be assessed by both clinical and laboratory monitoring. If comparisons are performed between groups, then Barnard's exact unconditional test will be performed for binary variables and t-tests (or Wilcoxon Rank Sum as appropriate) for continuous measures.

Reactogenicity

The number and percentage of participants experiencing each type of reactogenicity sign or symptom will be tabulated by study group and severity. Exact 95% Clopper-Pearson confidence intervals will be calculated for each set of events. For a given sign or symptom, each participant's reactogenicity will be counted once under the maximum severity for all assessments.

Adverse Experiences

Adverse experiences are coded into Medical Dictionary for Regulatory Activities (MedDRA) system organ classes and preferred terms. The number and percentages of participants experiencing each specific adverse event will be tabulated by dose level, severity and relationship to treatment. For the tabulation of the adverse experiences by system organ class, a participant was counted only once in a given body system. For example, a participant reporting gastritis and diarrhea will be reported as one participant, but the symptoms will be listed as two separate AEs within the class. A complete listing of adverse experiences for each participant will provide details including preferred term, system organ class, severity, relationship to treatment, onset time, duration and outcome.

Local Laboratory Values

Boxplots of local laboratory values will be generated for baseline values and for values measured during the course of the study. Each boxplot will show the 1st quartile, the median, and the 3rd quartile. Outliers, or values outside the boxplot, will also be plotted. If appropriate, horizontal lines representing boundaries for abnormal values will be plotted. Tables will be provided for changes from baseline.

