Grade 4 (Potentially Life-threatening): Hospitalization; immediate medical intervention or therapy required to prevent death.

Grade 5 (Death): Death is assigned a Grade 5 severity.

Only the single adverse event that is assessed as the primary cause of death should be assigned “grade 5” severity.

**Toxicity Grading Scale for Healthy Adult and Adolescent Volunteers Enrolled in
Preventive Vaccine Clinical Trials
Modified from FDA Guidance - September 2007**

A. Tables for Clinical Abnormalities

Local Reaction to Injectable Product	Mild (Grade 1)	Moderate (Grade 2)	Severe (Grade 3)	Potentially Life Threatening (Grade 4)
Pain	Does not interfere with activity	Repeated use of non-narcotic pain reliever > 24 hours or interferes with activity	Any use of narcotic pain reliever or prevents daily activity	Hospitalization
Tenderness	Mild discomfort to touch	Discomfort with movement	Significant discomfort at rest	Hospitalization
¹ Erythema/Redness	2.5 – 5 cm	5.1 – 10 cm	> 10 cm	Necrosis or exfoliative dermatitis requiring medical attention
² Induration/Swelling	2.5 – 5 cm and does not interfere with activity	5.1 – 10 cm or interferes with activity	> 10 cm or prevents daily activity	Necrosis requiring medical attention
³Vital Signs				
	Mild (Grade 1)	Moderate (Grade 2)	Severe (Grade 3)	Potentially Life Threatening (Grade 4)
⁴ Fever (°C) (°F)	38.0 – 38.4 100.4 – 101.1	38.5 – 38.9 101.2 – 102.0	39.0 – 40 102.1 – 104	> 40 > 104
Tachycardia - beats per minute	101 – 115	116 – 130	> 130	Hospitalization for arrhythmia
⁵ Bradycardia - beats per Minute	50 – 54	45 – 49	< 45	Hospitalization for arrhythmia
Hypertension (systolic) - mm Hg	141 – 150	151 – 155	> 155	Hospitalization for malignant hypertension
Hypertension (diastolic) - mm Hg	91 – 95	96 – 100	> 100	Hospitalization for malignant hypertension
Hypotension (systolic) – mm Hg	85 – 89 and symptomatic	80 – 84 and symptomatic and requiring oral fluids	< 80 and symptomatic and requiring IV fluids	Hospitalization for hypotensive shock
⁶ Respiratory Rate – breaths per minute	17 – 20	21 – 25	> 25	Intubation

1. In addition to grading the measured local reaction at the greatest single diameter, the measurement should be recorded as a continuous variable.
2. Induration/Swelling should be evaluated and graded using the functional scale as well as the actual measurement.
3. Subject should be at rest for all vital sign measurements.
4. Oral temperature; no recent hot or cold beverages or smoking.

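### The diary card takes only a centimetre figure for swelling and redness, so by itself it cannot separate 'none' from 'not measured' or supply the functional swelling grade that Appendix 6 requires

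*Combined protocol and SAP*

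**What the plan says.** Section 3.1 makes the occurrence of solicited local signs and symptoms over seven days a primary endpoint. Section 8.3.2 tabulates each sign by group and severity, and says that each participant's "reactogenicity will be counted once under the maximum severity for all assessments".

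The diary card (Appendix 10) has eight daily pages: the day of vaccination and Days 1 to 7. Local pain and the general symptoms have None, Mild, Moderate and Severe cells. Swelling and redness have one centimetre blank each:

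- Swelling: "Please record in cm, the largest width measurement of the swelling".
- Redness: "Please record in cm, the largest width measurement of the redness".
- Measuring instruction: "Measure the swelling (raised area) and the redness (red area) separately and record each measurement on the diary card".

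The injection-site scale at the foot of the page does mention arm use, but its graded anchors describe pain, for example "notable pain; some limitation of use of arm". On the last page a column is headed "Maximum severity after day 7 (Mild, moderate or severe", yet the swelling and redness rows under it again hold only centimetre blanks.

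In Appendix 6, Table A, swelling reaches Grade 2 or 3 by size or by effect on activity, and Grade 1 needs both the size and no interference. Footnote 2 adds: "Induration/Swelling should be evaluated and graded using the functional scale as well as the actual measurement". Redness Grades 1 to 3 rest on diameter alone.

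Under Section 5.3.1 the participant supplies answers from memory when "injection site symptom information (except swelling or redness measurements) is missing from the diary cards". The two measurements are thus left out of the repair step.

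**The concern.** The grading rule needs two pieces of information on swelling, and the daily instrument asks for one. Grading from the card alone can place activity-limiting swelling too low.

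Separately, a participant with no swelling or redness has no box to tick and no instruction to write a zero. A blank may mean that nothing was there or that nobody measured. Section 8.3.2 does not say how a blank is counted, so an unstated rule would decide the rate.

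Both problems touch a primary endpoint with 20 participants per group. The grade also matters during the trial, because Section 7.2 has reactogenicity forms reviewed against the pause rules and Section 7.5 uses Grade 3 or 4 events. Neither kind of information can be reliably recovered once the diary week is over.

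**Working it through.** **1. Swelling grade from centimetres alone against Appendix 6.** Inputs are the Table A bands: 2.5–5 cm Grade 1, 5.1–10 cm Grade 2, above 10 cm Grade 3; interference with activity Grade 2; prevention of daily activity Grade 3. The Appendix 6 grade is the higher of the size grade and the functional grade.

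| Swelling | From cm alone | Appendix 6, no interference | Appendix 6, interferes | Appendix 6, prevents daily activity |
|---|---|---|---|---|
| 1 cm | no grade | no grade | 2 | 3 |
| 3 cm | 1 | 1 | 2 | 3 |
| 7 cm | 2 | 2 | 2 | 3 |
| 11 cm | 3 | 3 | 3 | 3 |

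The centimetre grade is never above the Appendix 6 grade. For activity-limiting swelling of 10 cm or less it can fall short by one to three levels.

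**2. The plan's own precision figure.** For 0 events in n participants, the exact two-sided 95% upper limit is 1 − 0.025^(1/n). With n = 20 this is 1 − 0.025^(1/20) = 16.8%, which agrees with Table 4 in Section 8.2.1.

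**3. Effect of the unstated rule for blanks.** The documents give no rate of blank lines, so the number b is an assumption, shown over a range. Take one group of 20, no recorded swelling, and b participants whose swelling line is blank throughout. For x > 0 the Clopper-Pearson limits are the 2.5% quantile of Beta(x, n − x + 1) and the 97.5% quantile of Beta(x + 1, n − x).

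| b (assumed) | Blank = none | Blank excluded | Every blank a reaction |
|---|---|---|---|
| 1 | 0/20, upper 16.8% | 0/19, upper 17.6% | 1/20 = 5% (0.1–24.9%) |
| 2 | 0/20, upper 16.8% | 0/18, upper 18.5% | 2/20 = 10% (1.2–31.7%) |
| 3 | 0/20, upper 16.8% | 0/17, upper 19.5% | 3/20 = 15% (3.2–37.9%) |
| 4 | 0/20, upper 16.8% | 0/16, upper 20.6% | 4/20 = 20% (5.7–43.7%) |
| 5 | 0/20, upper 16.8% | 0/15, upper 21.8% | 5/20 = 25% (8.7–49.1%) |

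Moving from 'none' to 'missing' changes the upper limit modestly. The last column is the extreme bound, not an expectation.

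**The case against.** The strongest reply is that the card is only a memory aid (Section 5.3.1) and not the sole source. Section 5.1 lists physical assessment by clinicians beside it. Appendix 1 schedules interim history, targeted examination and diary review at Days 3 and 7. Section 5.3.2 asks participants with significant impairment of daily living to come in. Section 7.2 has investigators determine severity and refers to separate reactogenicity forms that the documents do not show. Section 8.3.2 counts all assessments. The recall exclusion covers measurements, so asking whether swelling was present or limiting is not clearly barred.

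Much of this stands. A reader might infer that the functional information is never collected and that swelling cannot be graded at all. The documents do not support that: clinicians could obtain the information, and a participant may write 0.0 unprompted. What remains is that no section requires the functional question to be asked or its answer recorded. The prompt to attend is also set at significant impairment, while Grade 2 needs only interference.

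Four other readings go too far:

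- **That a blank defaults to no reaction.** Section 8.3 defines who is analysed, not how a blank is counted. The plan is silent, so the direction of any error from blanks is unknown.
- **That reactions below 2.5 cm are lost.** Footnote 1 of Appendix 6 keeps the measurement as a continuous variable. Only their place in the severity table is open.
- **That redness lacks a functional grade.** Its Grades 1 to 3 need none; redness shares only the problem of blanks.
- **That the pause rule would miss events.** This depends on reactogenicity forms that cannot be seen.

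The card's pictures and the training content are also not shown, so a zero-entry instruction there cannot be excluded. A lost 'None' box is unlikely, because the same layout repeats on all eight pages.

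**Conclusion.** The point holds for the diary card used as written. The card does not separate 'none' from 'not measured' for swelling or redness, and it does not supply the functional grade that Appendix 6 requires for swelling. Clinician review at Days 3 and 7 may fill part of the gap, but nothing in the plan obliges it to.

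Under-grading from centimetres alone can only go downward, by up to three levels for swelling of 10 cm or less. How often it would occur is unknown. The range for blanks rests on an assumed number of blank lines and on a counting rule that the plan does not state. The change is worth making because it concerns data that analysts could not reliably reconstruct later.

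**What to change.** **Diary card, every daily page:**

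- Add a 'None (0.0 cm)' tick box to the swelling line and to the redness line.
- Add one tick line for swelling: no interference, interferes with activity, or prevents daily activity.

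**Grading:** grade swelling by the worse of size and function. Appendix 6 already requires this; the new line supplies the missing input.

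**Section 8.3.2:** state that a swelling or redness line left blank is counted as missing, not as none.

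**Cost:** a slightly longer card that must be reprinted and re-approved, two or three extra database fields, and one sentence in the analysis section. Reported local reaction grades may rise, because function-limiting swelling would then carry its Appendix 6 grade.
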